In what follows we therefore distinguish between primary aims, secondary aims, and exploratory analyses. The Steering Committee has determined that none of these analyses will be adjusted for multiple comparisons. Instead we will make clear in our papers our *a priori* hierarchy of analysis aims and focus on the presentation of effect size estimates and confidence intervals. Although we will present 95% confidence intervals, the papers will include standard errors for our effect size estimates so that readers can compute broader confidence intervals if desired.

ABSOLUTE VS. PERCENT CHANGE

We will focus on absolute weight change, but will likely present key analyses with percent change as well. When computing percent change, the relevant absolute weight changes will always be expressed as a percent of entry weight. In this way all weight changes, regardless of how they are expressed, will be additive over time. This in turn will provide some convenient equivalencies for model fitting as noted below. For simplicity, in this document we will simply speak of weight change without specifying whether this is absolute weight change or percent weight change.

PRIMARY AIMS

- 1. Determine, among those willing to continue after the initial 30-months of intervention, the effect on weight of an additional 30-months of PC intervention (PC-Active) compared to no further PC intervention (PC-Control).**

This question very specifically takes the health plan perspective and asks, among the subset of PC participants who want to continue in such an intervention after an initial 30 months, whether doing so for an additional 30 months has any further benefit. The analysis will therefore focus on the 196 PC participants from Baton Rouge, Baltimore, and Durham who were re-randomized into phase 3. However it also will include the 208 IT participants from these sites who were re-randomized so that a single “unified” model will thus allow us to test this primary aim as well as a secondary aim of interest (see aim #8).

We will assume an ITT analysis and use imputed values for all participants who do not provide a FU60 weight measurement.

Outcome variable = change in weight from R2 to FU60 ($\Delta W_{R2-FU60}$).

Analytic model:

$$\Delta W_{R2-FU60} = \beta_0 + \beta_1 PCA + \beta_2 ITA + \beta_3 \Delta W_{E-R2} + \sum \beta_i X_i, \quad (1)$$

where PCA and ITA are binary indicators of the PC-Active and IT-Active conditions, respectively, and the X_i s are a series of adjustment variables that include indicators for the four race-gender groups and for site. Since weight changes are additive over time, this model can be rewritten as

$$\Delta W_{E-FU60} = \beta_0 + \beta_1 PCA + \beta_2 ITA + \beta_3^* \Delta W_{E-R2} + \sum \beta_i X_i, \quad (2)$$

where $\beta_3^* = (\beta_3 + 1)$. The other coefficients in the two models are identical. Thus so long as we condition on change in weight from entry through R2, it makes no difference if we use as our outcome phase 3 weight change or total weight change over the 66 months since entry. The primary aim is evaluated by testing whether $\beta_1 = 0$.

2. Compare the 60-month weight loss maintenance experience of participants in the PC-Active intervention versus those in the SD condition.

Unlike the previous analysis, which was limited to (i.e., conditioned on) those who were re-randomized into phase 3, this “unconditional” analysis will look at all PC and SD participants, regardless of their phase 3 consent status. However we will still exclude Portland participants. Similar to aim 1, we will fit a unified model that allows us to test both PC and IT related hypotheses, so that the analysis will actually include all 740 participants from Baton Rouge, Baltimore, and Durham who were initially enrolled into phase 2, including those randomized to the IT condition.

For the PC participants, we will effectively assume not that they were randomized to a single 30-month PC intervention, but rather that they were randomized to one of two 60-month interventions (PC-Active or PC-Control). Since assignment to these latter two arms was done at random, the 3-arm randomization framework is valid so long as we retroactively “randomize” those PC participants who opted out of phase 3 (or provided a “data only” consent) into either the PC-Active or PC-Control conditions. 18% (44/240) of the PC participants from these two sites will need to be randomized in this manner.

Similar considerations hold for the IT arm, 18% of whom (46/254) will need to be retroactively randomized.

We will use an ITT analysis and use imputed values for all participants who do not provide a FU60 weight measurement.

Outcome variable = change in weight from R1 to FU60 ($\Delta W_{R1-FU60}$).

Analytic model:

$$\Delta W_{R1-FU60} = \beta_0 + \beta_1 PCA + \beta_2 PCC + \beta_3 ITA + \beta_4 ITC + \beta_5 \Delta W_{E-R1} + \sum \beta_i X_i, \quad (3)$$

where PCA, PCC, ITA, and ITC are 0/1 indicators of the PC-Active, PC-Control, IT-Active, and IT-Control conditions, respectively, and the X_i s are indicators for the four race-gender groups and for site. Since weight changes are additive over time, this model can be rewritten as

$$\Delta W_{E-FU60} = \beta_0 + \beta_1 PCA + \beta_2 PCC + \beta_3 ITA + \beta_4 ITC + \beta_5^* \Delta W_{E-R1} + \sum \beta_i X_i, \quad (4)$$

where $\beta_5^* = (\beta_5 + 1)$. The other coefficients in the two models are identical. Thus so long as we condition on phase 1 weight change, it makes no difference if we use as our outcome phase 2 plus phase 3 weight change or total weight change over the 66 months since entry. Aim #2 is evaluated by testing whether $\beta_1 = 0$.

SECONDARY AIMS

3. Compare the 60-month weight loss maintenance experience of the PC-Active versus PC-Control arms and of the PC-Control versus SD arms.

These analyses also can be tested using model (3). The β_1 - β_2 comparison tests PC-Active versus PC-Control, while β_2 alone is used to test PC-Control versus SD.

4. Determine, among those willing to continue after the initial 30-months of intervention, the effect on weight of an additional 12-months of IT intervention (IT-Active) compared to no further IT intervention (IT-Control).

Analogous to aim 1, this question asks, among the subset of IT participants who want to continue in such an intervention after an initial 30 months, whether doing so for an additional 12 months has any further benefit. The analysis will therefore be limited to the 277 IT participants from all four sites (i.e., including Portland) who were re-randomized into phase 3. It also will include the 277 PC participants from these sites who were re-randomized so that a single “unified” model can be fit that will allow us to test multiple hypotheses of interest.

We will assume an ITT analysis and use imputed values for all participants who do not provide a FU42 weight measurement.

Outcome variable = change in weight from R2 to FU42 ($\Delta W_{R2-FU42}$).

Analytic model:

$$\Delta W_{R2-FU42} = \beta_0 + \beta_1 PCA + \beta_2 ITA + \beta_3 \Delta W_{E-R2} + \sum \beta_i X_i, \quad (5)$$

where again the X_i s are indicators for the four race-gender groups and for site. Also as before, this model can be rewritten as

$$\Delta W_{E-FU42} = \beta_0 + \beta_1 PCA + \beta_2 ITA + \beta_3^* \Delta W_{E-R2} + \sum \beta_i X_i, \quad (6)$$

where $\beta_3^* = (\beta_3 + 1)$ and the other coefficients in the two models are identical. Aim #4 is evaluated by testing whether $\beta_2 = 0$.

5. Compare the 42-month weight loss maintenance experience of the IT-Active and IT-Control interventions versus each other and versus the SD condition.

The unconditional analysis used to address this aim will parallel that used to address aims #2 and #3, but focusing only on data through FU42. A unified model will again be fit so that we can address a similar aim related to the PC intervention arms. Since Portland participated in the FU42 data collection, the analysis will include all 1032 randomized participants. Hence all IT and PC participants from Portland who were not originally re-randomized (41/191) will also need to be retroactively re-randomized as was done for the other sites. All SD participants are included, though they don't require re-randomization per se.

We will use an ITT analysis and use imputed values for all participants who do not provide a FU42 weight measurement.

Outcome variable = change in weight from R1 to FU42 ($\Delta W_{R1-FU42}$).

Analytic model:

$$\Delta W_{R1-FU42} = \beta_0 + \beta_1 PCA + \beta_2 PCC + \beta_3 ITA + \beta_4 ITC + \beta_5 \Delta W_{E-R1} + \sum \beta_i X_i, \quad (7)$$

where PCA, PCC, ITA, and ITC are 0/1 indicators of the PC-Active, PC-Control, IT-Active, and IT-Control conditions, respectively, and the X_i s are indicators for the four race-gender groups and for site. Since weight changes are additive over time, this model can be rewritten as

$$\Delta W_{E-FU42} = \beta_0 + \beta_1 PCA + \beta_2 PCC + \beta_3 ITA + \beta_4 ITC + \beta_5^* \Delta W_{E-R1} + \sum \beta_i X_i, \quad (8)$$

where $\beta_5^* = (\beta_5 + 1)$ and the other coefficients in the two models are identical. Tests of $\beta_3 = 0$ and $\beta_4 = 0$ are used to evaluate the IT-Active vs. SD and IT-Control vs. SD contrasts, respectively, while a test of $\beta_3 - \beta_4 = 0$ is used to evaluate the IT-Active versus IT-Control contrast.

6. Compare the 42-month weight loss maintenance experience of the PC-Active and PC-Control interventions versus each other and versus the SD condition.

Model (7) is also used to test these contrasts. Tests of $\beta_1 = 0$ and $\beta_2 = 0$ are used to evaluate the PC-Active vs. SD and PC-Control vs. SD contrasts, respectively, while a test of $\beta_1 - \beta_2 = 0$ is used to evaluate the PC-Active versus PC-Control contrast.

7. Compare the 42-month weight loss maintenance experience of the PC-Active and IT-Active interventions.

Model (7) is also used to test this contrast as well. The relevant test is $\beta_1 - \beta_3 = 0$.

8. Determine, among those willing to continue after the initial 30-months of intervention, the effect on weight at 60 months of an additional 12 months of IT intervention (IT-Active) compared to no further IT intervention (IT-Control).

This is the analog of aim #4 for FU60. Due to the fact that the IT-Active intervention was not continued beyond FU42, this aim will only be evaluated if we see a significant effect in aim #4. It can be evaluated by testing $\beta_2 = 0$ in model (1).

9. Compare the 60-month weight loss maintenance experience of the PC-Active and IT-Active interventions.

This is the analog of aim #7 for FU60. Due to the fact that the IT-Active intervention was not continued beyond FU42, this aim will only be evaluated if we see a significant effect in aim #7. It can be evaluated by testing $\beta_1 - \beta_3 = 0$ in model (3).

EXPLORATORY ANALYSES

Additional exploratory analyses that are planned include subgroup analyses and correlates of 5-year weight change.

Power

Due to the now pilot nature of the Phase III analysis, with a very wide measurement window no power calculations are presented for this analysis.

References

1. National Institutes of Health. NHLBI clinical guidelines on the identification, evaluation, and treatment of overweight and obesity in adults, executive summary. 1998. U.S. Department of Health and Human Services.

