Cultural training. The Minority Implementation Committee organizes and conducts a minority training program for all trial interventionists. This training program focuses on the cultural differences of African Americans and European Americans and the ways in which the maintenance interventions (both the initial weight-loss program and the subsequent maintenance interventions) can be best adapted to the needs and expectations of both groups.

8. Randomization

Following completion of Phase I (initial weight-loss program), those participants who have lost at least 4 kg are eligible to be randomized for Phase II. Prior to randomization, study staff reconfirm eligibility (table 2), review the study requirements with the participant, answer questions, administer the randomization consent, and collect baseline data (section 10, table 4).

Randomization assignments are generated on-site using software developed by the Coordinating Center. These assignments are stratified by clinic, race (African-American vs. non African-American), and weight loss during phase I. Allocation assignments are also blocked within these categories to provide a balance in treatment assignments over time. As part of the randomization process, the computer program verifies eligibility and the completeness of entry and baseline data. Individuals lacking proper documentation of eligibility or key data elements are not randomized.

Participants learn their treatment assignment from a staff member who is not involved in follow-up data collection.

Blinding

WLM study participants know their intervention assignments, as do clinical center staff that are involved in delivering the interventions. However, all clinical center staff involved in follow-up data collection are kept blinded to participants' treatment assignments, and all intervention staff are kept blinded to participants' official study measurements. Participants receive a complete set of weight measurements, along with a summary of their other clinical measurements and their laboratory measurements, at the conclusion of their follow-up period.

9. Maintenance interventions (Phase II)

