The trial’s primary specific aim is to compare the effectiveness of each of two active interventions (PC and IT) versus self-directed/usual care in maintaining weight loss from randomization (R, at the end of the initial Phase I weight-loss phase of the trial) to the end of Phase II maintenance (F), 30 months post randomization. We use E to denote an entry measure (beginning of weight-loss program, or Phase I), e.g. W_E .

Formal hypotheses:

Null hypothesis: The PC [IT] intervention does not differ from SD/UC in the change in weight over the 30-months maintenance period; this is a joint hypothesis with two parts: $\beta_1 = 0$ and $\beta_2 = 0$.

Alternate hypothesis 1. The PC intervention differs from SD/UC in the amount of weight change over the 30-months maintenance period: $\beta_1 \neq 0$ (2-sided test).

Alternate hypothesis 2. The IT intervention differs from SD/UC in the amount of weight change over the 30-months maintenance period: $\beta_2 \neq 0$ (2-sided test).

The full model for the primary hypothesis test is

$$\Delta W_{R-F} = \beta_0 + \beta_1 PC + \beta_2 IT + \beta_3 \Delta W_{E-R} + \beta_4 W_E + \sum \alpha_i S_i + \sum \delta_i E_i + e_{ij} \quad (1)$$

where PC is an indicator of the personal contact intervention; IT is an indicator of the Web-based intervention; ΔW_{E-R} indicates the change in weight from Entry to Randomization, and W_E is the Entry weight. The S_i terms are indicators of the performance sites, the E_i terms are planned additional explanatory variables, and e_{ij} is a random “error” term assumed to be normally distributed with mean zero. The additional explanatory (E’s) factors are 1) age, 2) female gender, 3) African-American ethnicity, and 4), gender x ethnicity interaction.

Under this model, β_1 represents the effect, after adjusting for all of the explanatory factors, of the PC intervention vs. SD/UC, and β_2 represents the corresponding contrast for the IT vs. SD/UC groups. Tests of the null hypotheses that $\beta_1 = 0$ and $\beta_2 = 0$ are thus the test of the primary hypothesis. Because the PC vs. IT contrast is a secondary aim, a test of the null hypothesis that $\beta_2 - \beta_1 = 0$ is done only if at least one of the previous two null hypotheses is rejected.

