Finally, in the stratum of individuals without the risk factor at baseline, we will evaluate the relative risk of developing the risk factor (incident cases, defined by medication use or elevation of the corresponding physiologic measurement). We will compare arms within each stratum using a chi-square test.

Aim 6. Compare the effects of PC, IT, and SD/UC on measures of behavior change (e.g., physical activity, aspects of diet).

The following alternative hypotheses will be evaluated against the null hypothesis of no difference between treatment group and SD/UC.

- The PC intervention produces greater behavior change than does SD/UC
- The IT intervention produces greater behavior change than does SD/UC

Aim 7. Compare the effects of PC, IT, and SD/UC on weight change **from entry** (prior to Phase I) to the end of the post-randomization maintenance phase (Phase II).

While change in weight from R to F is of primary interest, comparison of the change in weight from initial entry (E) to final assessment (F) is an additional study aim. The logic behind this aim is that, if the maintenance interventions are successful in maintaining all or some of the original weight loss, then some of the original weight loss should persist to some extent through the end of the trial. The analytic model for this analysis is

$$\Delta W_{E-F} = \beta_0 + \beta_1 PC + \beta_2 IT + \beta_4 W_E + \sum \alpha_i S_i + \sum \delta_i E_i + \varepsilon, \quad (2)$$

using the same conventions and statistical approaches as for Model 1. The imputed 30-month weights will be used in this analysis.

Secondary Covariate Analyses

The analyses in this section are motivated by an interest in factors that may moderate weight loss in the various treatment groups.

Aim 4. Compare the effects of PC, IT, and SD/UC on weight maintenance in **subgroups defined by race, sex, age, and baseline body mass index.**

Comparison of treatment effects across subgroups defined by race, sex, age, baseline body mass index, and potentially additional factors, will be approached using the same analytic model (1), with added terms to elucidate possible differential effects between subgroups, operationalized as interactions between treatment group indicators and subgroup indicators. The model is:

$$\Delta W_{R-F} = \beta_0 + \beta_1 PC + \beta_2 IT + \beta_3 \Delta W_{E-R} + \beta_4 W_E + \sum \gamma_i [XI_k]_i + \sum \alpha_i S_i + \sum \delta_i E_i + e_{ij} \quad (3)$$

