All individuals who were randomized to PC or IT in Phase II were re-randomized for Phase III, using a randomization scheme blocked by site, Phase II treatment group, and Phase II weight change. PC participants were re-randomized to continued intervention (PC-active) or to no further intervention (PC-control). Similarly, IT participants were re-randomized to continued intervention (IT-active) or to no further intervention (IT-control). Individuals were only informed of their new randomization assignment after they signed Phase III consent. SD participants were re-enrolled in their current control condition (SD). Individuals who do not enroll in Phase III were asked to sign a separate consent allowing us to conduct a final outcome assessment (weight measurement and an adverse events questionnaire). Thus all participants who re-enroll were included in analyses for Aims 1 and 2, above, and all participants who were originally randomized into Phase II will be included in analyses for Aims 3 and 4.

Phase III Intervention

Overview. The Phase III active interventions (PC-Active and IT-Active) are extensions of their Phase II counterparts that were designed to support the participants' behavioral self-management programs. Rather than simply supplying information or giving instruction on diet and exercise, they provide personal accountability, prompting and reinforcement for behaviors that support continuing efforts to maintain weight loss or lose more weight. Both the Phase III active PC and IT interventions were designed to be practical, easy to implement in a variety of settings, and amenable to broad dissemination.

As a part of the randomization process, we conducted an orientation session for all participants explaining their new study assignment. This included an intervention orientation for IT-active

and PC-active participants, and discussion of the importance of follow-up data collection for the IT-control and PC control participants.

Self-Directed (SD) control condition: Phase III participants in the self-directed control condition did not receive lifestyle change counseling in Phase III, but returned for data collection visits.

PC-Control and IT-control: Participants randomized from PC into PC-control and from IT into IT-control receive no further intervention during Phase III, but will return for data collection visits.

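### Aim 7's Model (2) leaves out the Phase I weight change, so it re-estimates the primary contrasts with a larger standard error than necessary

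*Combined protocol and SAP*

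**What the plan says.** Section 8 (Randomization) describes the Phase II assignments: "These assignments are stratified by clinic, race (African-American vs. non African-American), and weight loss during phase I".

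Section 12, Primary Analysis statistical model, regresses the randomisation-to-final change on arm, two weight terms, site, age, gender, race and the gender-by-race interaction. The weight terms are defined there: "ΔW_{E-R} indicates the change in weight from Entry to Randomization, and W_E is the Entry weight".

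Section 12, Aim 7, says that "comparison of the change in weight from initial entry (E) to final assessment (F) is an additional study aim". Model (2) has the entry-to-final change as outcome. Its covariates are those of Model (1) without the Phase I change. The text says that conventions and approach otherwise follow Model 1, and gives no reason for the omission.

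Section 15, Phase III Primary Aim 2, states the relevant algebra: "Thus so long as we condition on phase 1 weight change, it makes no difference" whether the outcome is counted from the first randomisation or from entry.

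For Phase III, re-randomisation was "blocked by site, Phase II treatment group, and Phase II weight change". Phase III Models (1), (2), (5) and (6) carry the change from entry to second randomisation as one term. Models (3), (4), (7) and (8) carry the Phase I change. The other covariates are "indicators for the four race-gender groups and for site".

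**The concern.** A stratification factor that also predicts the outcome belongs in the analysis model. If it is left out, its variance stays in the residual, and the model-based standard error takes no credit for the balance that stratification achieved. Here the omitted variable is also an additive component of the Aim 7 outcome, so its share of the variance need not be small.

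The plan would then report two estimates, two intervals and two p-values for the same treatment effect, one pair from Model (1) and a less precise pair from Model (2). If Model (1) is significant and Model (2) is not, a reader could conclude that the interventions preserved weight since randomisation but not since entry. That difference would come only from the covariate set.

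**Working it through.** **1. The two models share a parameter.** Write P for the Phase I change and D for the randomisation-to-final change, so that entry-to-final change = P + D. If Model (1) holds for D with coefficient β3 on P, then P + D follows the same equation with coefficient 1 + β3 on P and the same β1 and β2. P is fixed before randomisation, so omitting it does not bias β1 or β2. With P included, the contrasts and standard errors for P + D equal those for D. A simulation (2,000 runs, N = 800) gave a largest difference in the PC coefficient below 1e-12, with equal average standard errors. Multiple imputation does not disturb this, because only the 30-month weight is imputed and the identity holds within each imputed dataset.

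**2. Reproduce the plan's own figure.** Detectable effect = SDE × (z for α + z for power). For SDE 0.60 and two-sided α = 0.025 (the first Holm step):
- power 0.80: 0.60 × (2.241 + 0.842) = 1.85 kg (Table 5: 1.8)
- power 0.85: 0.60 × (2.241 + 1.036) = 1.97 kg (Table 5: 2.0)
- power 0.90: 0.60 × (2.241 + 1.282) = 2.11 kg (Table 5: 2.1)

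So the SDE is the standard error of one arm contrast. Section 12 (Detectable effects/sample size) derives it from PREMIER with entry weight and the 6-month change in the model. It therefore describes a Model (1)-type analysis, not Model (2).

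**3. Residual SD.** Assuming equal allocation (800/3 = 266.7 per arm), σ = SDE / √(2/266.7):
- SDE 0.45 (PREMIER, 12 vs 6 months): 5.2 kg
- SDE 0.52 (PREMIER, 18 vs 6 months): 6.0 kg
- SDE 0.60 (illustrative row): 6.9 kg

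**4. Inflation in Model (2).** SE ratio = √(1 + ((1 + β3) × s / σ)²), where s is the SD of P given the other covariates. Neither s nor β3 is in the documents. Section 15 gives a mean Phase I loss of 8.4 kg, and eligibility requires at least 4 kg. An exponential excess above 4 kg would have SD 8.4 - 4 = 4.4 kg. The ranges below are assumptions.

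| σ (kg) | s (kg) | β3 = 0 | β3 = -0.25 | β3 = -0.5 |
|---|---|---|---|---|
| 5.2 | 3 | 1.155 | 1.090 | 1.041 |
| 5.2 | 5 | 1.388 | 1.233 | 1.110 |
| 6.0 | 3 | 1.118 | 1.068 | 1.031 |
| 6.0 | 4 | 1.202 | 1.118 | 1.054 |
| 6.0 | 5 | 1.301 | 1.179 | 1.083 |
| 6.9 | 3 | 1.090 | 1.051 | 1.023 |
| 6.9 | 5 | 1.233 | 1.137 | 1.063 |

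At central values (σ = 6.0, s = 4, β3 = -0.25) the ratio is √(1 + (0.75 × 4 / 6)²) = √1.25 = 1.118, so the SE is 0.58 instead of 0.52 kg. The ratio is 1 only if β3 = -1. The simulation with s = 4.4 gave 0.593 against 0.520, or 14% larger.

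**5. Effect of the stratification.** The number of weight-loss strata is not given, so 2, 3 and 4 were tried (σ = 6.0, s = 4.4, β3 = -0.25). Model (2) reports an SE of about 0.59, while its estimate varies with an SD of about 0.54 to 0.57. Its type I error at nominal 5% is roughly 3% to 4%. With P added, reported SE and sampling SD agree at about 0.52, and type I error is close to 5%.

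**6. Phase III, for scale.** All inputs are assumed.
- Adding entry weight: ratio √(1 + (slope × SD / σ)²), with slope 0.01 to 0.10 kg per kg, SD 12 to 18 kg and σ 6 to 7 kg. Omission widens intervals by 0.01% to 4.4%, and by at most 1.1% for slopes up to 0.05.
- Splitting the entry-to-second-randomisation change, with σ = 6 kg and part SDs of 3 and 5, 4 and 6, or 5 and 7 kg: for a coefficient gap of 0.1 to 0.5 the gain is 0.1% to 5.6%.
- No estimate was made for age.

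**The case against.** The strongest reply is that the repair yields no new information. Once the Phase I change is in Model (2), its contrasts duplicate the primary test, so the efficient estimate is already reported. Aim 7 stands under Other aims in section 2, and section 12 names the change from randomisation as the one of primary interest. Model (2) is unbiased and errs on the conservative side. All of this is correct, and it lowers the severity. It does not remove the point: the plan would still publish a second, wider interval and a conservative p-value for the same parameter. Nor should the inflation be read as lost sample size for the trial, since Model (1) already recovers that precision.

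A reader might infer that section 15 contradicts Model (2). It does not. The equivalence there is conditional on adjusting for Phase I change, and Model (2) does not adjust. Section 15 is also a later plan.

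A reader might also infer that the Phase III models ignore the weight variables used in randomisation. The documents do not support that. Phase III Models (3), (4), (7) and (8) include the Phase I change itself. Models (1), (2), (5) and (6) include the entry-to-second-randomisation change, which contains the Phase II change used for blocking. Entry weight and age are absent from the listed terms, but neither was a stratifier, and for Model (1) the adjustment list is introduced as what the variables include, so it may not be exhaustive. A short covariate set is a legitimate choice for an extension that the plan describes as now pilot in nature.

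**Conclusion.** The point holds for Aim 7's Model (2), at low severity. The model omits a stratification factor that the primary model includes and that is part of its own outcome. The consequence is a standard error about 2% to 39% larger than needed, about 12% at central values, and a conservative test. Nothing is biased and the primary analysis is untouched. That Model (2) targets the same contrasts as Model (1) is algebra and needs no assumption. The size rests on equal allocation and on assumed values for the SD of Phase I loss and for β3.

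For Phase III there is only an optional refinement. The stratified weight terms are already in the models, directly or within the composite, and the expected gain is at most a few percent of the standard error on assumed inputs.

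**What to change.** In section 12, Aim 7, add the entry-to-randomisation weight change to Model (2). State that the PC and IT contrasts are then identical to those of Model (1), so no separate test is implied. Report Aim 7 as adjusted mean entry-to-final change by arm, with those contrasts beside it. This answers the question Aim 7 asks, namely how much of the original loss persists.

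Optional for section 15: in Phase III Models (1), (2), (5) and (6), split the entry-to-second-randomisation change into its Phase I and Phase II parts, so that the blocking variable has its own coefficient. Entry weight and age may be added for consistency with the Phase II model. Do not add the Phase II change to Models (3), (4), (7) or (8), because there it comes after the randomisation being analysed.

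The covariates are already collected, so the cost is a few lines of SAP wording and no new data.
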